APPENDIX E

Vaccine Report Card

Dear Study Participant,

Thank you for your willingness to participate in this clinical trial of the MUC1 vaccine. This is one of the first cancer prevention vaccine trials, and we want to carefully document the vaccine experience.

In this booklet you will find a “vaccine report card” to record symptoms. Please review these instructions carefully. If you have any questions about the report card, ask your study team.

When to record symptoms:

The day of your first vaccine injection will be considered Day 0.

- On Day 2, please record symptoms you have experienced since you left your study visit. If you took any medications to relieve symptoms, please write them down. If the symptoms have disappeared, write down the date on the report card in the column labeled “date symptoms disappeared.” Once a symptom disappears, you do not need to continue recording anything about that symptom.
- On Day 7, write down all of the symptoms you experience from Day 3 to Day 7.
- On Day 14, write down all of the symptoms you experience from Day 8 to Day 14.
- If you are not scheduled to return for a study visit on or around Day 14, please send this booklet back to the study team by mail, fax, or email. Your study team members will provide an envelope, fax number, or email address for you.

What to record:

The pilot studies have shown us that some, but not all people receiving the vaccine will have reactions such as redness at the injection site, swelling, warmth or itching, and pain or tenderness. Not everyone experiences these symptoms. Some people will have no symptoms.

If there are any other symptoms you experience and want to document, please write them in the text box on the back page of this booklet.

About Injection Site Reactions

Measuring the size of the redness (erythema):

This picture shows redness of the skin. To measure this, use a tape measure or ruler to measure the maximum distance from one side of the red patch to the other in centimeters. It might be helpful to measure it across the red patch both from side to side and from top to bottom. Record the longest distance.

Pain and Tenderness:

You may experience pain at the injection site. There are two possible types. One is general muscle pain or achiness at the site that is present even when you're not touching the area, such as with movement or even sitting. The other type is tenderness, which is pain when you touch the injection site. Please record these separately.

Swelling or Induration:

Swelling or induration is firmness, like the bump that may be experienced after a mosquito bite. The easiest way to measure it is to use your fingertip to feel the edge of the firmness, and then make a mark with an ink pen at one edge. Make another mark at the opposite edge. It might be helpful to measure and mark the swelling or induration both from side to side and from top to bottom. To measure this, use a tape measure or ruler to measure the maximum distance between the two marks in centimeters. Record the longest distance.

Warmth and itching:

Document when warmth or itching begins and when these symptoms go away.

Your Signature

Date

Study Coordinator Signature

Date

MAY2013-01-01, “ Randomized, Double-Blind, Placebo-Controlled Trial of MUC1 Vaccine in Patients with Newly Diagnosed Advanced Adenomas”

Vaccine Report Card

Participant ID _____ **Date of Injection** _____

Instructions: Please complete this “report card” at 2 days, 7 days, and 14 days after your injection. Bring it to your next study visit or return it to the study team by mail, fax, or email.

Possible side effects	Date Symptom Appeared	2 days after injection Date _____	7 days after injection Date _____	14 days after injection Date _____	Date Symptom Disappeared
Redness at the injection site		 None  Yes. It measured _____ centimeters	 None  Yes. It measured _____ centimeters	 None  Yes. It measured _____ centimeters	
Pain at the injection site without touching		 None  A little, but it didn’t interfere with normal activity  Some, required OTC* medications for more than 24 hours or limited normal activity  A lot, required prescription medications, interfered with normal activity  Required ER visit or hospitalization	 None  A little, but it didn’t interfere with normal activity  Some, required OTC* medications for more than 24 hours or limited normal activity  A lot, required prescription medications, interfered with normal activity  Required ER visit or hospitalization	 None  A little, but it didn’t interfere with normal activity  Some, required OTC* medications for more than 24 hours or limited normal activity  A lot, required prescription medications, interfered with normal activity  Required ER visit or hospitalization	

Possible side effects	Date Symptom Appeared	2 days after injection Date _____	7 days after injection Date _____	14 days after injection Date _____	Date Symptom Disappeared
Tenderness (Pain at the injection site with touch)		 None  A little, but it didn't interfere with normal activity  Some, required OTC* medications for more than 24 hours or limited normal activity  A lot, required prescription medications, interfered with normal activity  Required ER visit or hospitalization	 None  A little, but it didn't interfere with normal activity  Some, required OTC* medications for more than 24 hours or limited normal activity  A lot, required prescription medications, interfered with normal activity  Required ER visit or hospitalization	 None  A little, but it didn't interfere with normal activity  Some, required OTC* medications for more than 24 hours or limited normal activity  A lot, required prescription medications, interfered with normal activity  Required ER visit or hospitalization	
Swelling/ Induration**		 None  Yes. It measured _____ centimeters	 None  Yes. It measured _____ centimeters	 None  Yes. It measured _____ centimeters	
Itching at site		 None  Yes	 None  Yes	 None  Yes	
Skin warmth at site		 None  Yes	 None  Yes	 None  Yes	

* OTC – Over the counter medications such as Tylenol® or ibuprofen.

** Firm, raised swelling.

If you experience any other symptoms that you would like to report, please make note of them on this page. Be sure to write down the date the symptom appeared and the date the symptom disappeared. If you took any medications for the symptom or visited a doctor or hospital for the symptom, please inform the study team.

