6.2 Reported Adverse Events and Potential Risks

The side effects listed in the table below are based on a variety of previous studies that were similar to this study in some ways but different in important ways (including stronger doses) that may have led to different side effects. In the previous study that was most similar to this study, no autoimmune disease or serious side effects were identified.

Possible Side Effects of the MUC1 – poly-ICLC vaccine:

Common, Some May Be Serious In 100 people who receive the injection, more than 20 may have:

• Redness at injection site (erythema)• Pain/soreness at injection site• Flu-like symptoms, which may include fever chills, headache, fatigue, muscle pain, and joint pain• Night sweats• Loss of appetite• Low albumin blood test result (a type of protein in the blood)

The redness and soreness generally resolve within a few days to a week. Generally, acetaminophen (Tylenol®) is sufficient for pain relief. The flu-like symptoms generally resolve within 12-24 hours. Acetaminophen (Tylenol®) generally helps with these symptoms if they occur.

Occasional, Some May Be Serious In 100 people who receive the injection, 4 to 20 may have:

• Low white blood cell count (cells that fight infections)• Low platelet count (cells that help the blood clot in order to stop bleeding)• Anemia (which may cause tiredness, or may require blood transfusion)• Abnormal liver function test results

Rare, Some May Be Serious In 100 people who receive the injection, 3 or fewer may have:

• Hives, shortness of breath, or an allergic reaction that is life-threatening• Immune reaction to his or her own tissue (autoimmune diseases) or if present, may be made worse.

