13.6 Reporting and Exclusions

All randomized participants who are evaluated at week 0 and week 12 and have IgG values from those time points will be evaluable for the primary endpoint of this study using the intent-to-treat principle. We plan to over randomize assuming 10% drop out within 1 year to ensure an adequate sample size in the primary analysis cohort. There will be no imputation for missing data. A summary and listing of all major protocol violations will be provided. All details will be given in the final study report and/or manuscript. Participants lost to follow-up will be censored on the last date of assessment (or contact) and as appropriate for analyses that are dependent upon length of study participation.

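### The Vaccine Report Card gives conflicting instructions on what to record after a symptom clears and does not say which size to enter, so peak size or a recurrence can go unrecorded

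*Combined protocol and SAP*

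**What the plan says.** The part of Appendix E on when to record symptoms gives four instructions that matter here.

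- Day 2 entry: "On Day 2, please record symptoms you have experienced since you left your study visit".
- Same bullet, on symptoms that have gone: "If the symptoms have disappeared, write down the date on the report card in the column labeled" for disappearance dates, and then "Once a symptom disappears, you do not need to continue recording anything about that symptom".
- Day 7 entry: "On Day 7, write down all of the symptoms you experience from Day 3 to Day 7".
- Day 14 entry: "On Day 14, write down all of the symptoms you experience from Day 8 to Day 14".

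The card itself is to be filled in "at 2 days, 7 days, and 14 days after your injection", and its columns are headed by those time points. Each symptom row has a 'None' box at each entry, one column for the date of appearance and one for the date of disappearance. Redness and swelling have one centimetre value per entry. The measuring instructions ask for the longest distance, meaning the longest diameter across the lesion, not the largest size over time.

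Section 11.1.3.2 grades redness by diameter (Grade 1: 2.5 to 5 cm; Grade 2: 5.1 to 10 cm; Grade 3: above 10 cm), grades swelling by diameter and function, and keeps the redness measurement as a continuous variable too. Sections 1.2, 8.2 and 13.5 (item 5) list the participant-reported reactions as a secondary objective or endpoint, summarized descriptively and compared between arms.

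**The concern.** The Day 7 and Day 14 bullets describe interval records: everything that happened since the previous entry. The stop-recording sentence releases the participant from further entries about a symptom that has gone. The column heads can be read in a third way, as the state on that day. Two careful participants with the same reaction could therefore return different cards.

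This matters most for reactions that clear between entries. Section 6.2 says of the vaccine: "The redness and soreness generally resolve within a few days to a week". Clearing after the Day 2 entry and before the Day 7 entry is therefore ordinary timing. At stake are the maximum diameter, the worst pain or tenderness category, and any second episode.

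**Working it through.** There is no plan figure to reproduce and no arithmetic beyond reading the grade table. The check sets the card's instructions against the kinds of cell they can produce.

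1. **'None' ticked.** Absence is recorded, though the card does not say whether it means absent on that day or absent for the whole window.
2. **Blank after a completed disappearance date.** The symptom had resolved by that date. If the date is Day 6, however, the blank Day 7 cell covers a window in which the symptom was mostly present. The date preserves occurrence and duration, but not diameter or severity category.
3. **Blank with no disappearance date.** Absence cannot be told from non-completion, and the documents give no rule for reading such a cell.
4. **Symptom that begins and ends inside Days 3 to 7 or 8 to 14.** The interval bullets ask for it and the date columns can hold it. It is recorded if the bullets are followed; the stop sentence, read literally, excuses it.
5. **Reaction present on Day 2 that enlarges and clears before Day 7.** The interval bullet asks for it and the stop sentence excuses it. Even a participant who records it is not told which size to enter.
6. **Symptom that goes and returns.** The interval bullets ask for it, the stop sentence excuses it, and there is only one pair of date columns.

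**Effect on the grade, with assumed sizes for one participant.** Take redness of 4 cm on Day 2, 11 cm on Day 4, and gone on Day 6.

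- Largest size in the window recorded: 11 cm is above 10 cm, so Grade 3.
- Nothing recorded after it disappeared: only 4 cm remains, which lies in 2.5 to 5 cm, so Grade 1.
- Size on the entry day: Day 7 is 'None' and again only 4 cm remains, so Grade 1.

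The third line shows that deleting the stop sentence is not enough. The card must also say which size is wanted.

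**Whether other collection recovers the loss.** Section 7.3 has staff compare measurements at the Week 2 and Week 12 visits, but only for reactions still present. No such comparison is described after the Week 2 or Week 53 injections. The standard adverse event form (section 11.1.3.1) covers injection site reactions by CTCAE grade. The diameter-based grading in section 11.1.3.2 is tied to the card and its separate form.

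**The case against.** The strongest reply is that the stop sentence applies only after a symptom has gone. It does not excuse an ongoing reaction, and the interval bullets run without a gap and ask for everything in between. On that view, a lost peak comes from the single undated size field. This is half right. The size field is a separate defect, and a participant who follows the bullets will report that the reaction occurred. But entries are made looking back on three days only. By Day 7 a reaction that cleared on Day 6 has already disappeared, and the general wording of the stop sentence then excuses the entry.

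It is also fair that the past-tense answer options suit interval recall, that adverse events are collected separately, and that the separate card form and the data management plan, which might say how blanks are handled, are not among the documents.

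Three stronger readings are tempting and are not supported.

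- *No blank can be told from 'None'.* The card has a 'None' box at every entry, and a blank after a disappearance date shows resolution by then. The ambiguity is limited to blanks without a date.
- *Missing cells fall mainly in the vaccine arm and bias the comparison.* This is plausible against a saline placebo, but there are no completion data or day-by-day reaction rates. Any percentage would rest on invented counts.
- *Section 13.6 turns permitted blanks into missing data.* The sentence "There will be no imputation for missing data" sits in a paragraph about evaluability for the primary IgG endpoint. Reading absence from a recorded stop date is derivation, not imputation.

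**Conclusion.** The point holds in a limited form. The instructions conflict, the required size is undefined, a second episode has no place on the card, and a blank without a disappearance date has no stated meaning. Each can lose or blur information, and the first two can lower a diameter-based grade, by two grades in the assumed example.

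The size of any bias cannot be computed. The documents do not say how often reactions grow after Day 2, how often symptoms return, or how participants read the card. Section 6.2 supports the timing of resolution only, not growth after Day 2.

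The consequence is confined to the card data. These are summarized descriptively, called exploratory in section 13.7, and kept outside the minimum data set by section 11.1.3.2. The primary endpoint is unaffected, and the stopping rule in section 13.7.1 does not refer to the card. This is a worthwhile, inexpensive correction to a form, not a threat to the trial's conclusions.

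**What to change.** In Appendix E:

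- Delete the sentence that lets participants stop recording.
- At each entry, ask for the largest diameter and the worst severity since the previous entry, even if the symptom has gone.
- Say that 'None' is ticked only if the symptom was absent for the whole interval, and that no cell is left blank.
- Ask for a returning symptom to be recorded again, and add a second pair of appearance and disappearance dates.
- Head the columns Days 0-2, Days 3-7 and Days 8-14.

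The cost is one revision of a participant form and its matching case report form, with slightly more burden: a few more ticks, and sometimes a measurement between entry days. A largest size reported at the next entry will rely partly on recall, which is still better than no value.

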APPENDIX F

NAFLD Activity Score

The Non-Alcoholic Fatty Liver Disease (NAFLD) Activity Score (NAS) is a validated score that is used to grade disease activity in patients with NAFLD. The NAS is the sum of the biopsy's individual scores for steatosis (0 to 3), lobular inflammation (0 to 2), hepatocellular ballooning (0 to 2), and fibrosis (0 to 4). An NAS of 1 or 2 corresponds to NAFL, 3 to 4 corresponds to borderline NASH, and a score ≥ 5 corresponds to NASH. (See "[Histologic scoring systems for chronic liver disease](#)", section on '[Nonalcoholic fatty liver disease](#)'.)

Please note that for this protocol, the calculation of the NAS applies only for the determination of eligibility for individuals with a diagnosis of Non-Alcoholic Steatohepatitis (NASH).
